Pressure Algometer –

For pressure pain testing, we will use a standard mechanical pressure algometer (Wagner Instruments).

Anxiety measures

All groups will be assessed for anxiety with questionnaire methods using the Social Interaction Anxiety Scale (SIAS)¹⁶. The SIAS measures anxiety with respect to social interactions. It is one of the more often-used self-report measures of social anxiety, with numerous evidence-based studies demonstrating its reliability and construct validity¹⁷. The SIAS contains 20 items which are rated from 0 (not at all characteristic or true of participant) to 4 (extremely characteristic or true of participant). Items are self-statements describing one's typical cognitive, affective, or behavioral reaction to a variety of situations requiring social interaction in dyads or groups (e.g., going to a party, talking to an attractive member of the opposite gender, expressing one's feelings).

5. Sample selection and size

Healthy adults will be recruited for participation in this study. The PAR-Q and You form and the AHA screening questionnaire will be administered during the screening process to determine whether potential subjects meet the inclusion/exclusion criteria.

Inclusion criteria include:

- Between age 18-40
 - Normal BMI (18.5-25)
 - HR 60 to 100
 - BP less than or equal to 140/90
- *HR and BP will be taken as part of the screening process to determine eligibility and also taken at the beginning of each exercise session.

Exclusion criteria include as indicated by the PAR-Q and You and AHA screening forms:

- Age less than 18 or greater than 40 years
- Cardiac, respiratory, neurological or musculoskeletal disease
- Acute pain
- Chronic pain condition
- Diabetes
- BMI ≥ 25.1 or ≤ 18.4
- Regular participation in high intensity athletic/sporting activities
- Sedentary
- Anxiety or depression disorders.
- Tape allergy
- Currently pregnant

A power analysis of pain outcome indicates that a minimum of 10 people/condition will be sufficient to detect statistical differences in our primary dependent variable (pain sensitivity), but to account for variability, our recruitment goal is 15 people/condition. When 10 participants per group have completed the study, a preliminary analysis will be conducted for statistical power, if we reach 0.80, recruitment will stop.

6. Recruitment of subjects

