The collection of data has been described in detail under "Procedures". The primary outcome is a change in Quantitative Sensory Testing. This includes a series (8) of Quantitative Sensory Tests measured at baseline and at the completion of the 1-week intervention period. These tests are measured at two sites (calf and forearm). Significant differences between groups for 7 of the tests (per body site) will be identified using a one-way ANOVA comparing percent change from baseline (post-test (i.e. day 6)/baseline test (i.e. day 0)). Given the number of statistical tests that will be required for the primary outcome measurements, $p < 0.01$ will be utilized for each body site. An additional test for mechanical sensitivity will be measured at each site using a rank sum test at $p < 0.05$.

The secondary outcomes for this study include (1) HR during exercise, (2) Borg RPE before and after exercise and (3) testing "acute" effects of exercise on QST testing. HR during exercise and Borg RPE are measured to make sure that exercise causes a change in HR and/or perceived exertion. HR and Borg RPE data will be analyzed using percent change from start of exercise (post-exercise/pre-exercise) with two-way ANOVA for 3 treatment groups (3-day, 5-day, 10 day) across time (day 1, 3, 5) with an adjusted p value of $p < 0.03$. Control group will not be included in that analysis as HR was not measured on the control days and perceived exertion is at "0" on all days. For acute effects of exercise, participants were given 8 QST tests (on each forearm and calf) 5 min and 30 min after each exercise (or control session) on days 1, 3, and 5. Significant differences between groups for these tests (per body site) will be identified using a two-way MANOVA comparing percent change from baseline (post-exercise/baseline test (i.e. day 0)) across the three days (day 1, day 3, day 5) and at the 5 min and 30 min time QST measuring point. Given the number of statistical tests ($n=8$) that will be required for the QST secondary outcome measurements, $p < 0.01$ will be utilized for each body site.

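### Section 5 stops recruitment at 10 per group if power reaches 0.80, but leaves open the effect, endpoint and alpha; computed from observed differences, the rule is only a p-value cutoff

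*Combined protocol and SAP*

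**What the plan says.** Section 5 (Sample selection and size) reports that a power analysis found "a minimum of 10 people/condition will be sufficient to detect statistical differences in our primary dependent variable (pain sensitivity"), and adds that "to account for variability, our recruitment goal is 15 people/condition". It then sets an interim look: "When 10 participants per group have completed the study", "a preliminary analysis will be conducted for statistical power, if we reach 0.80, recruitment will stop". No effect size, SD, alpha or named test is given for the figure of 10 or for the look.

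Section 8 (Collection of data and method of data analysis) defines the primary outcome as eight sensory tests at two body sites, compared as day 6 over day 0. For most of them, "Significant differences between groups for 7 of the tests (per body site) will be identified using a one-way ANOVA", and because of the number of tests "required for the primary outcome measurements, $p < 0.01$ will be utilized for each body site". For the eighth, "An additional test for mechanical sensitivity will be measured at each site using a rank sum test", at 0.05. That makes 14 ANOVAs at 0.01 and 2 rank sum tests at 0.05. Section 8 neither mentions the interim look nor adjusts for it.

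**The concern.** The final sample size depends on a calculation whose inputs are not written down. Two analysts following Section 5 on the same data could reach opposite decisions.

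There are two readings. In the first, power is computed from the group differences seen at 10 per group. Observed power is then a one-to-one function of the p-value, so the rule stops when the result is significant enough. A trial that stops could report 0.80 power that the design does not have, and its effect estimate would be selected for being large. In the second, only the SD is updated and the effect is one planned beforehand. That is an ordinary sample-size check, but a reader cannot verify it without the planned effect, endpoint and alpha.

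Two gaps affect both readings. The alpha matters because the same effect can reach 0.80 at 0.05 and fall well short at 0.01. The endpoint matters because a stop triggered by one test fixes the sample size for the other 15.

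**Working it through.** **Inputs from the documents.** Four groups; look at 10 per group (N = 40, df 3 and 36); goal 15 per group (N = 60, df 3 and 56); primary alphas 0.01 and 0.05. Equal allocation is assumed from the equal numbers per condition. No effect size is given, so Cohen's f is an assumption throughout (two extreme groups, two at the mean), shown over a range.

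**1. The plan's own figure.** Ten per condition cannot be reproduced, because its inputs are not stated. Solving backwards, the noncentrality λ that gives 80% power with df 3 and 36 is 18.14 at alpha 0.01 and 12.16 at 0.05. With f = √(λ/N):
- alpha 0.01: √(18.14/40) = 0.67
- alpha 0.05: √(12.16/40) = 0.55

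At 15 per group the corresponding values are 0.53 and 0.44. Whether 10 is sufficient therefore depends on an effect and an alpha that the text does not give.

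**2. Observed power as a p-value cutoff.** Two formulas for the observed noncentrality are in use.

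| Formula | Alpha 0.01 | Alpha 0.05 |
|---|---|---|
| λ = 3F | F ≥ 18.14/3 = 6.05, p ≤ 0.0019 | F ≥ 12.16/3 = 4.05, p ≤ 0.014 |
| λ = N·SSB/SSW = (40/36)·3F | F ≥ 5.44, p ≤ 0.0034 | F ≥ 3.65, p ≤ 0.021 |

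The simulations below use λ = 3F. The two rank sum tests are not covered by this equivalence.

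**3. What stopping shows (observed-difference reading, check and test at 0.01).**

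| Assumed f | True power, n = 10 | Trials that stop | Overstatement of extreme-group difference in stopped trials |
|---|---|---|---|
| 0.25 | 7% | 2% | 118% |
| 0.40 | 25% | 11% | 57% |
| 0.55 | 56% | 33% | 27% |
| 0.67 | 80% | 59% | 13% |

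Part of this overstatement would remain without the rule. Had the same trials continued to 15, it would shrink by 10/15; at f = 0.40, 57% × 10/15 = 38%.

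**4. Overall effect with matched alpha.** Type I error per test goes from 0.010 to 0.011, or from 0.050 to 0.056. At alpha 0.01, power at f = 0.40 is 46.5% with the rule against 46.0% with fixed n = 15. Average bias over all trials at alpha 0.01 is 1–3%. Among significant results, the overstatement with the rule against fixed n = 15 is 29% against 25% (f = 0.40), 10% against 7% (f = 0.55) and 4% against 1% (f = 0.67).

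**5. Mismatched alpha.** With the check at 0.05 and the ANOVA at 0.01, type I error is about 0.016. The critical F at 0.01 is 4.38, so 4.05 ≤ F < 4.38 stops the trial without significance. At f = 0.40, about 30% of trials stop, and 4% of all trials stop with p above 0.01. On either reading, an effect with 80% power at 10 per group and alpha 0.05 (f = 0.55) has 56% at 0.01.

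**6. SD-only reading, planned effect correct.** The check stops when the within-group SD estimate is small enough, with probability P(χ²₃₆ ≤ 36·(f/f₈₀)²), where f₈₀ is the 80%-power value from step 1. This is 51% at f = 0.67, alpha 0.01, and 52% at f = 0.55, alpha 0.05. Overall power is 92% and 90%, against 96% and 95% with fixed n = 15. Null rejection is 0.011 and 0.055.

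**7. Primary tests left at 10.** At alpha 0.01, a test held at 10 instead of 15 per group has power 25% against 46% (f = 0.40), or 56% against 83% (f = 0.55).

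**The case against.** The strongest reply is that Section 5 describes a check of power, not of efficacy. It follows a prior power analysis and gives variability as the reason for 15, which fits an SD update. This stands as a plausible reading, and under it the harm is small. It does not settle the matter: a rule that stops when power is reached in a preliminary analysis can as naturally mean observed power, and no planned effect is written down to rule that out. A reader might go further and infer that the SD version could not be carried out at all. The text does not support that, because a power analysis is reported as done and the investigators may hold its inputs. What can be said is that the check cannot be verified from the text.

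Second, even on the observed-difference reading the damage is limited. This stands. With matched alpha the cutoff is stricter than significance itself, and most of the overstatement among significant results comes from low power rather than from the rule.

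Third, Section 5 refers to pain outcomes. In the primary analysis only the tactile threshold test, described elsewhere as not painful, uses 0.05, so the text points towards 0.01. This weakens the mismatch scenario without excluding it: Section 4 lists tactile sensitivity among the pain measures, and Section 5 names no alpha.

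**Conclusion.** The point holds as an under-specified interim stopping rule. The effect used, the triggering test and the alpha are all left open, and Section 8 is silent on the look. If power comes from the observed differences, reaching 0.80 is a p-value cutoff and is not evidence of 80% power. At an assumed f = 0.40 and alpha 0.01, about one trial in nine would stop although true power is 25%.

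A reader might infer that the plan contains an efficacy stop that seriously inflates type I error. The documents do not support that: the observed-difference reading is possible but not stated, and the inflation with matched alpha is about 0.001 per test at 0.01 or 0.006 at 0.05. Nor does the text say that any single test can trigger the stop; the loss of power on the other primary tests is conditional on that.

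The sizes rest on assumed f values, equal groups, normal data and one ANOVA endpoint at a time. The defect should be fixed, but it is not fatal.

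**What to change.** In Section 5, do not compute the check from observed group differences. Choose one of two options:

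1. Delete the stop, recruit to the stated goal of 15 per condition, and run one final analysis.
2. Keep a check that updates only the SD, against an effect, a named primary endpoint and that endpoint's Section 8 alpha, all fixed now. The SD may be the pooled within-group SD or the blinded total SD. The total SD exceeds the within-group SD by a factor √(1 + f²), which is 1.08 at f = 0.40 and 1.20 at f = 0.67. If the planned effect is true, the blinded version would therefore rarely stop at 10: about 5% of trials at f = 0.67, alpha 0.01, and 13% at f = 0.55, alpha 0.05.

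Under either option, state the effect, SD, alpha and endpoint behind the claim that 10 per condition is sufficient. If the look is kept, describe it in Section 8.

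The cost is wording, plus at most 4 × 5 = 20 participants whom an early stop might have saved. All are within the existing goal.

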Title Page:

Study Protocol

Managing Pain: Testing the dosing and social aspects of exercise therapy using a multi-school collaborative approach with human participants.

NCT number not available

6/2/16

Protocol Summary Form

Managing Pain: Testing the dosing and social aspects of exercise therapy using a multi-school collaborative approach with human participants.

1. Statement of the research question

What is the effect of exercise dose and social interactions on the ability of exercise to reduce acute pain in healthy human participants?

2. Purpose and significance of the study

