Chronic pain is a serious problem in the US that affects 116 million adults¹. Chronic pain (e.g. fibromyalgia, chronic lower back pain) can be linked both epidemiologically and biologically with major depressive disorder (MDD) and various anxiety disorders. Rates of MDD, depressive, or anxiety symptoms in patients with chronic pain are very high (13-82%)^{2,3}. As such, the treatment options for patients with pain AND behavioral abnormalities have focused on agents that target this comorbidity. One type of non-pharmacologic therapy that has shown promise in chronic pain is exercise. Regular physical activity and exercise improves many aspects of a person's general health, including cardiorespiratory function, mental health, and pain. Despite the purported benefits of exercise, 1 in 3 Americans are sedentary and do not meet the activity guidelines developed by the Surgeon General⁴ (moderate intensity exercise, 30 minutes per day, 5 days per week). Sedentary behaviors are more prevalent in persons with chronic pain. Exercise therapy is an attractive therapy for chronic pain because of its low cost and ability to reduce sedentary behavior, depression, and pain^{5,6,7}. One of the challenges at both the research and clinical level in implementing exercise as a therapy are the numerous variables inherent in prescribing exercise to patients with pain which include the best dose of exercise and social anxiety surrounding exercise. Walking has been emphasized because it is an easy exercise that most people can accomplish without special equipment or training. The 2008 Physical Activity Guidelines⁴ suggest that even light physical activity is better than none for improving health. Especially for those persons with chronic pain, it may be most beneficial to begin a physical activity exercise protocol at a lower intensity and/or dose and increase physical activity as tolerated. Before a recommendation of low-dose or low-intensity exercise can be made, it is necessary to determine if physical activity at these lower levels will also provide the benefit of exercise-induced analgesia.

In this study we will examine the effect of dose related to exercise therapy for pain in healthy adult humans. We will be using an acute pain model to study the effect of exercise dose on pain. Acute pain models are currently used to study pain (both acute and chronic) in human samples as there is currently no chronic pain model.

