We hypothesize that therapy done at a low dose will produce the best cost-to-risk ratio for patients.

3. Research design and procedures

This study is designed as a randomized controlled trial with repeated measures.

Aim – the effect of exercise dose on pain: subjects will be randomly assigned to one of four exercise groups: 1.) no exercise (control); 2.) low dose exercise (3x/week); 3.) moderate dose exercise (5x/week); 4.) high dose exercise (10x/week).

The co-primary investigators (co-PI's) will be involved in the procedures listed below. Graduate research students will assist with recruitment, data collection, and data processing. A PhD student in the Biology department ([name]) will assume primary responsibility for data collection. The graduate students will be trained on all procedures involved in this study by the co-PI's. Prior to data collection, the prospective subjects will complete a full screening, using a checklist of the inclusion/exclusion criteria and the PAR-Q and AHA health questionnaires (see Instruments) to determine eligibility. The purpose of the study, the methods of data collection and all potential risks will be verbally communicated to prospective subjects at the

initiation of the first data collection session (Day 0) (Figure 1). Prospective subjects will be given an approved informed consent form to read and sign. Subjects will then complete the International Physical Activity Questionnaire long form (IPAQ-long) to assess baseline level of daily physical activity and the Social Interaction Anxiety Scale (SIAS) for a measure of participant's anxiety. The researcher will explain the questionnaires to subjects and will be available to answer any questions while the subjects complete these forms. Basic health information obtained from the subject will assess whether the subject has been diagnosed with any cardiac, respiratory, neurological or musculoskeletal disorder, chronic pain or currently has acute pain. Subjects who report any of the above medical diagnoses or pain during screening will be excused from participation in the study, but will receive compensation for attending the screening session. Any identifying information used to determine eligibility, including the checklist of inclusion/exclusion criteria and the health questionnaires, will be destroyed.

[figure not shown]

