Figure 1: Study Design. Subjects will be randomly assigned to the control, low- dose exercise, or high-dose exercise group. Intervention will occur on Days 1-5 depending on group assignment. Assessment of physical and pain measures occurs on Days 1, 3, 5, and 6.

Subjects will then be set-up for training on the exercise protocol, physical pain measures and pedometer use. Subjects will become familiarized with the exercise protocol, including the physiological measures to be assessed [heart rate (HR)], the Borg Rate of Perceived Exertion (RPE) Scale, and the treadmill speed at which they will be walking (3.5mph). Typical walking speed to engage in moderate intensity physical activity (3-5.99 METs) is a brisk pace of 3-4 mph and anticipated activity heart rate will be 60% of age-adjusted maximal heart rate⁸. The subject will walk on the treadmill for 5 minutes to become comfortable with the exercise procedure. Subjects will be instructed to step up onto the treadmill and stand on the sides not the belt or belt deck. The researcher will slowly raise the speed to 2 mph. The subject will be instructed to step on the treadmill at this time. After 30 seconds, the speed will be ramped up to 2.5 mph and after another 30 seconds, the speed will be ramped up to their prescribed session speed. They will also be instructed to walk with a natural gait pattern, allowing bilateral arm swing. To allow a natural arm swing, subjects are unable to hold onto the treadmill arm rails. Subjects will be introduced to the Borg RPE scale and asked to provide subjective feedback on their level of exertion at the initiation of and during the final minute of this 5-minute training period. Subjects will be given a standard pedometer and instructed to wear it on their wrist during all hours (except showering/bathing) for the 6 consecutive days during the week in which they participate in data collection. The digital screen will be covered as awareness of daily step counts may influence participant's normal daily physical activity. Subjects will be given an instruction sheet for testing sessions and pedometer use.

During the enrollment period subjects will also be given a full description of all sensory and pain measures that will be taken. With initial consent, all subjects will be allowed to experience all sensory/pain measures before full enrollment. All sensory and pain assays are

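### For 7 of the 8 primary QST tests per site the plan names only an omnibus ANOVA, so the low dose is not separately tested against control

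*Combined protocol and SAP*

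**What the plan says.** The primary outcome in section 8 is a set of eight QST measures at each of two sites (calf and forearm), compared between day 6 and day 0. For seven of them the analysis is: "Significant differences between groups for 7 of the tests (per body site) will be identified using a one-way ANOVA". The level is p<0.01, and the reason given is "Given the number of statistical tests that will be required for the primary outcome measurements". The eighth measure, mechanical sensitivity, gets a rank sum test at p<0.05, and the groups it compares are not named.

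No other analysis fills the gap:
- The two-way ANOVA for heart rate and perceived exertion leaves the control group out.
- The MANOVA for acute effects names no pairs.
- The later one-way ANOVA concerns baseline variables.

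The questions are set earlier. Section 1 asks about "the ability of exercise to reduce acute pain in healthy human participants". Section 2 says that before low-dose exercise is recommended, "it is necessary to determine if physical activity at these lower levels will also provide the benefit of exercise-induced analgesia". The aim in section 3 is broader: "the effect of exercise dose on pain: subjects will be randomly assigned to one of four exercise groups".

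**The concern.** The F-test asks whether four means are equal. It has no direction and does not point to a group. The purpose in section 2 needs a directional statement about one group: low-dose exercise compared with no exercise. If the plan is followed as written, a significant result leaves that statement to a reading of the group means, with no test, interval or error rate behind it.

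The silence also leaves room for choice. Four groups give 4×3/2 = 6 pairs per QST test. Which pairs to examine, at what level and with what adjustment could all be settled after the data are seen. The 0.01 level does not close this gap, because the plan ties it to the number of QST tests.

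**Working it through.** **Inputs from the document.** Four groups (section 3); a minimum of 10 and a goal of 15 per group (section 5); ANOVA level 0.01 (section 8). Section 5 gives no effect size or SD, so its minimum of 10 cannot be reproduced. The two group sizes serve here only as inputs.

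**Assumptions.** Normal outcomes, equal SD, equal arms, and effects in SD of the analysed outcome. The document supplies none of these.

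**1. What a significant F can distinguish.** Power depends on λ = n·Σ(μᵢ − μ̄)².
- Only the high dose works by δ: μ̄ = δ/4, so the sum is 3(δ/4)² + (3δ/4)² = 0.75δ².
- All three doses work by δ: μ̄ = 3δ/4, so the sum is (3δ/4)² + 3(δ/4)² = 0.75δ².

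The two are identical. With δ = 1.4, λ = 15×0.75×1.96 = 22.05 at n=15 and 14.7 at n=10. The noncentral F (3 and 56, or 3 and 36 df) rejects at 0.01 with probability 91.2% and 68.0% in both cases. In one case the low dose does nothing and in the other it works fully, yet the planned test rejects equally often.

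**2. Error if follow-up is left open.** Suppose only the high dose works (1.4 SD). Control, low and moderate are then truly equal, which gives three null pairs. The F gate is passed in 91.2% of trials at n=15. Unadjusted tests at 0.01 on three pairs can err in at most 3×0.01 = 3%. Simulation (1,000,000 trials per scenario) gives the chance of a significant F with at least one false separation:

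| Follow-up level | n=15 | n=10 |
|---|---|---|
| 0.01 | 2.7% | 2.6% |
| 0.05 | 11.9% | 10.9% |

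If no dose works, the gate itself caps this at 1.0%.

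**3. Power of a specified comparison, low versus control.** The statistic is a t with pooled error, df = 4(n−1), and noncentrality δ√(n/2). At δ = 1.0 this is √7.5 = 2.74 (n=15) or √5 = 2.24 (n=10). At δ = 0.3 and n=15 it is 0.82.

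| | Dunnett, family-wise 0.01 | Single contrast at 0.01 |
|---|---|---|
| Critical value, n=15 / n=10 | 3.04 / 3.11 | 2.667 / 2.720 |
| Power at 1.0 SD, n=15 / n=10 | 39% / 21% | 53% / 33% |
| Power at 0.3 SD, n=15 | 1.7% | 3.8% |
| Effect for 80% power, n=15 / n=10 | 1.43 / 1.78 SD | 1.29 / 1.60 SD |

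**4. Reporting F and Dunnett together.** With each at 0.01 and no dose effect, at least one is significant in 1.45% of trials (n=15) or 1.44% (n=10).

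**5. Adding low versus moderate and low versus high.** Five comparisons at the Dunnett values of 3.04 and 3.11 have a family-wise error of about 1.6%. Holding 0.01 needs critical values of about 3.21 (n=15) and 3.29 (n=10).

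**The case against.** **The omnibus test fits the stated aim.** The one labelled aim is the effect of dose on pain, and an overall F-test answers whether response differs by group. This stands, and it is a reason to keep the ANOVA. The section 2 sentence is background rather than a formal hypothesis, but it gives the reason for studying low doses, and no planned test answers it.

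**The low dose is tested.** A reader might infer from the missing contrast that it is not tested at all. The document does not support that: the low-dose arm is in the four-group ANOVA and in the secondary MANOVA. The eighth measure's rank sum test might even be low versus control; its groups are unspecified, not excluded. What is missing is a separate test.

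**Error is already limited.** The F gate holds false separation to 1.0% when nothing works, and at the plan's own 0.01 level the figure is 2.7% in the scenario shown. That is modest. A reader might take 11.9% as the plan's error rate, but section 8 does not set 0.05 for these seven tests, and the plan commits to no follow-up at all.

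**The remedy may find nothing.** At 0.3 SD it almost certainly would not: 1.7% with Dunnett. The case for it is a defined basis for inference, not a promise of detection.

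**A dose trend would serve as well.** With ordered session counts a trend contrast suits the general aim, but a trend can be driven by the high dose and does not show that the low dose works.

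**The hypothesis asks something else.** Section 2 reads: "We hypothesize that therapy done at a low dose will produce the best cost-to-risk ratio for patients". That could be met by the low dose being similar to higher doses, which superiority contrasts cannot show. This is fair. That no endpoint measures such a ratio is a separate matter, as are the three-group caption to Figure 1 and the unsupported power statement.

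**Conclusion.** The point holds in limited form and should be corrected. For seven of the eight primary tests per site the plan pre-specifies no comparison of any dose with control, so the low dose is not separately tested and a significant result cannot be attributed to a dose. This rests on the text alone. The figures are illustrations under assumed effects, normality, equal SD and equal arms. They show that a high-only effect and an all-doses effect of the same size give the same chance of a significant F, and that open follow-up at 0.01 carries a false-separation rate of about 2.7% in one unfavourable scenario. They do not show serious error inflation in the plan as written. The unnamed groups in the eighth measure's rank sum test are the same omission in another form.

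**What to change.** In section 8:

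- **Seven ANOVA measures.** Keep the ANOVA as the global test. Pre-specify each exercise group versus control with Dunnett adjustment, family-wise 0.01 per QST test, and simultaneous confidence intervals. Report these whatever the F result, as the basis for any statement about a particular dose. Let F support only the global statement, because of the 1.45% in step 4.
- **If low dose is the only target.** A single pre-specified low-versus-control contrast at 0.01 is an acceptable and more powerful alternative.
- **General dose aim.** A dose-trend contrast may be added, but not in place of low versus control.
- **Eighth measure.** Name the groups compared and use a rank-based comparison with control that is adjusted for the number of doses.
- **If low is also to be compared with the other doses.** Control all five comparisons jointly, using the larger critical values in step 5.

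The change needs no new data. Its cost is the modest power in step 3, which should be stated openly. Making Dunnett conditional on a significant F would lower low-versus-control power further if all doses work by 1.0 SD: from 39% to 36% at n=15 and from 21% to 18% at n=10.
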